With our primary outcome we aim to capture pain that interferes with their everyday lives and collect the location of pain. The patient characteristics (exposures) are based on results from our systematic review(14), used in other studies (when including references).

The specific wording in the outcomes and throughout the questionnaire has been pilot tested among similar aged kids and adolescents.

Our secondary outcomes highlight the development or potential aggravated psychological and social factors related to musculoskeletal pain at follow-up.

Primary outcome

1) MSK pain influence

Q: Have you experienced pain in the past two weeks that have lead you to not being able to participate in play in the school yard or sparetime activities (ex. football or other sparetime activity)(38)?

If yes, we ask them to draw the area where they have experienced this pain with the following question:

Q: Draw on your body the areas you have had pain during the past two weeks (39).

These two questions will form our primary outcome and will be collected at all endpoints.

Secondary outcomes

1) Problemfilled MSK pain.

*Q: Draw a circle around the area of your body, where you have had the **most** problems with pain. You may only draw **one** circle.*

2) Pain intensity depicted on Faces Pain Scale Revised (FPS-R) or a 10 cm VAS scale for 8-11 and 12-19 year olds respectively (9).

Exposures

3) Self-reported anxiety.

Q: "Do you feel anxious"?

4) Self-reported depression (16).

Q: "Do you feel depressed"?

5) Self-reported low self-esteem (16).

Q: "Do you think that you have low self-esteem"?

6) Duration of troublesome pain episode (40, 41).

Q: "How long does a pain episode usually last"? (see appendix 1 and 2 for the Q in full length).

7) Frequency of troublesome pain episode (10, 42, 43).

Q: "How often do have a pain episode"? (see appendix 1 and 2 for the Q in full length).

8) Nervousness (41).

Q: "How often do you feel nervous"? (see appendix 1 and 2 for the Q in full length).

9) Higher disability index (12, 44).

Q's with yes/no answers:

1. is it difficult to fall asleep because of pain?

2. is it difficult to sit during a lesson?

3. does your pain disturb a walk longer than 1km?

4. does your pain disturb your physical exercise?

5. does your pain disturb your hobbies?

10) Higher HFAQ level (40).

Q: "Does your pain make any of the following activities difficult"?

1. reaching up to get a book from a high shelf

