2. carrying your school bag to school

3. sitting on a school chair for a 45 min. lesson

4. standing in a queue for 10 min.

5. sitting up in bed from a lying position

6. bending down to put your socks on

7. standing up from an armchair at home

8. running fast to catch a bus

9. sport activities at school

11) Tired during the day (42, 45).

Sample-size

The sample-size in this study was determined using the two following rationales: 1) a sample-size large enough to test and replicate the analyses from previous studies on. Given the prior odds (0.5, 1, 2) of follow-up MSK pain for patients, using estimates for the prognostic factors female sex, high disability index, multisite pain, and maximum HFAQ from our systematic review(14). We gained an estimate of P-values according to sample size, for all factors individually (Appendix 8). Sample size of 500 patients, would result in an estimate of P-values below 0.05 for all prognostic factors and 2) investigate a range of new prognostic factors related to the sparsely investigated ethnicity and socioeconomic status. As no one has yet tested any of these potential important prognostic factors, and never in a general practice setting, we decided on 500 subjects. The 500 subjects was decided based on 250 cases (we assume 50% will continue to experience pain at our primary follow-up time) giving approximately 125 cases per prognostic factor (500/number of prognostic factors). The results from this analysis will be considered as explorative as no studies have previously been conducted in a general practice setting. Again, assuming 50% has pain at follow-up and 20 events for each to be tested factor are needed. The model should allow for 10-15 variables in a multivariable logistic regression analysis. This would lead to a sample size of 480. Assumed, 5% is lost to follow-up and we have a sample-size of 504 included participants. Given the high prevalence of MSK pain at follow-up, this sample-size is feasible to include.

Questionnaires

We use three questionnaires in data collection of patient and parent characteristics: participant baseline questionnaire (Part-Quest-base) (Appendix 1), participant follow-up questionnaire (Part-Quest-follow-up) (Appendix 2), and the parent questionnaire (Pare-Quest) (Appendix 3).

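### The planned 480 evaluable participants support at most 12 model variables under the protocol's own rule, not the stated 10-15, and the 50% rate is not tied to the primary outcome

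*Protocol*

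**What the plan says.** The protocol's Sample-size section sizes the multivariable model by an events-per-variable rule. The inputs are "assuming 50% has pain at follow-up and 20 events for each to be tested factor are needed". The intended model size follows ("The model should allow for 10-15 variables in a multivariable logistic regression analysis"), then the result ("This would lead to a sample size of 480"), then an allowance for attrition: "Assumed, 5% is lost to follow-up and we have a sample-size of 504 included participants".

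Earlier in the same section the 50% is worded as "we assume 50% will continue to experience pain at our primary follow-up time". The primary follow-up is at 6 months. The section adds its own caveat: "The results from this analysis will be considered as explorative".

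The Outcomes section describes the primary outcome differently: "With our primary outcome we aim to capture pain that interferes with their everyday lives". Its first question concerns "pain in the past two weeks that have lead you to not being able to participate in play" or in spare-time activities. A body drawing follows for those who answer yes, and the two questions together form the primary outcome.

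**The concern.** The text presents the whole range of 10 to 15 variables as what 480 participants will support. A reader choosing the final model could therefore enter 15 variables and believe that the planned 20 events per variable had been kept.

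The second matter is the basis of the 50%. It is expressed as pain, with no source given at that point. The primary outcome is built on pain severe enough to stop play or spare-time activities. In Appendix 2 the two are separate items: item 5 asks where there has been pain, and item 6 asks whether it prevented participation. If the event counted in the model is a positive answer to item 6, its rate may differ from the rate of any pain, and the number of variables supported moves with it.

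**Working it through.** **Inputs, all from the Sample-size section:** event rate 50%; 20 events per variable; 10-15 variables; 480 evaluable; 5% loss; 504 included.

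**1. Reproduce the plan's figure.** Evaluable N = variables x 20 / 0.50.
- 10 variables: 200 / 0.50 = 400
- 12 variables: 240 / 0.50 = 480, the stated figure
- 15 variables: 300 / 0.50 = 600

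The stated 480 is reproduced only with 12 variables. The included number follows as 480 x 1.05 = 504, as stated.

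**2. What 480 delivers at 50%.** Events = 480 x 0.50 = 240.

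| Variables | Events per variable | Meets 20? |
|---|---|---|
| 10 | 24.0 | yes |
| 12 | 20.0 | yes |
| 13 | 18.5 | no |
| 14 | 17.1 | no |
| 15 | 16.0 | no |

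**3. Dependence on the rate.** Variables supported = 480 x rate / 20, rounded down. The rates below 50% are assumptions for illustration; the protocol gives none for the primary outcome at 6 months.

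| Rate | Events | Variables supported |
|---|---|---|
| 50% | 240 | 12 |
| 40% | 192 | 9 (9.6) |
| 30% | 144 | 7 (7.2) |
| 20% | 96 | 4 (4.8) |

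Ten variables need 200 events, so the lower end of the range fails below 200 / 480 = 41.7%.

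**4. The protocol's own range of scenarios.** Appendix 5 prints a two-factor example for MSK pain at follow-up: female sex, OR 1.78, fraction 0.5; problematic sleep, OR 1.68, fraction 0.2; factors independent. The overall rate is the weighted mean over the four combinations, ignoring the added random variation. At prior odds 0.5:

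0.4 x 0.333 + 0.4 x 0.471 + 0.1 x 0.457 + 0.1 x 0.599 = 0.427

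That is 480 x 0.427 = 205 events, which still supports 10 variables. The same calculation at prior odds 1 and 2 gives about 59% and 74%. These scenarios concern MSK pain, so they do not fix the rate of the activity-limiting outcome.

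**The case against.** The strongest reply is that 12 lies inside 10-15, so the sample size was derived for a model within the stated range. That stands: 480 and 504 are both consistent with 12 variables, and only 13-15 fall outside. Twenty events per variable is also a planning threshold that the protocol chose for itself, and nothing in the documents shows that 16 in place of 20 would do serious harm. The results are labelled explorative, and Appendix 5 calls its calculations provisional. These points limit the consequence. They do not make 480 support 15 variables.

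On the 50%, a reader might infer that the primary outcome must be rarer and that even 10 variables are out of reach. The documents do not support this. No passage gives a 6-month rate for the outcome, below 50% or otherwise. The lowest printed Appendix 5 scenario still supports 10 variables, and the other two lie above 50%. The 50% in the introduction is for still reporting pain after one year in 11-year-olds with weekly pain; the Sample-size section does not say that its 50% comes from there. The outcome definition also leaves some room: the stated objective speaks simply of pain at follow-up, and the drawing is part of the primary outcome. What stands is that the protocol does not say which outcome its 50% describes.

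A reader might also infer a shortfall because the Statistical methods section bases the primary analysis on first-time consulters. The protocol gives no share of such participants, so no shortfall can be shown. How model terms are counted and capped can be left to the statistical analysis plan.

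The aim of testing individual factors is little affected. For female sex (OR 1.78, half exposed, 480 evaluable, two-sided 5%), approximate power is 0.88, 0.86 and 0.81 at overall rates of 50%, 40% and 30%.

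**Conclusion.** The upper end of the stated model size is wrong on the protocol's own inputs. At 50% and 20 events per variable, 480 evaluable participants support at most 12 variables; 15 would have 16 events each, a fifth below the rule. This part is arithmetic and needs no outside assumption. It does not show that the study is too small, because the sample size is right for 12.

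The second part is a gap in the stated basis, not a demonstrated error. The rate is attached to continuing pain, while the primary outcome is built on activity-limiting pain with no 6-month rate given. Its effect on model size depends wholly on a rate that the protocol does not supply. The point is worth correcting, with modest consequence.

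**What to change.** In the Sample-size section:

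1. Replace the range of 10-15 variables with up to 12 variables at a 50% event rate. Keep 480 evaluable and 504 included.
2. State which outcome the 50% describes: any continuing pain, or the primary outcome as defined in the Outcomes section. If it is the former, give an assumed 6-month rate for the latter and mark it as an assumption.
3. Add the four-row table for 480 evaluable (50% = 12, 40% = 9, 30% = 7, 20% = 4), with the lower rates labelled as assumptions. Note that below 41.7% even 10 variables miss the rule, and that the lowest printed Appendix 5 scenario, about 43% for MSK pain at follow-up, still supports 10.

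The cost is a few sentences and a small table, with no new participants, data or outcomes. The downside is a slightly smaller stated model size.

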The GP screens the schedule for the day, and indicates eligibility with the word **MSK** written next to the patient name.

When consulting a patient with the indicated **MSK**, the GP is reminded to hand the patient the patient material. This can be done, prior, during or in the end of a consultation while the patient is getting dressed.

The patient hands in the completed questionnaire to an employee of the clinic, who stores it in a locked place. NP or her assistant will collect this in agreement with the clinic.

It is also possible for the GP to include a patient if MSK pain comes up during the consultation, without prior mentioning and hence unknown by the employee.

We will recruit patients from September 2018 to December 2019 and expect 500 participants in the ChiBPS cohort. If we are not able to recruit the number of participants according to our sample size calculations recruitment will continue until this number is reached.

Recruitment of parents

The child must first be included in the study in order for his/her parent(s) to be eligible. For included children, we will also request data from parents during a time window of two weeks from the time of Part-Quest receipt. We are not selective as to if and how many of the parents wish to participate. Parents declining participation will not cause withdrawal of the child's eligibility or inclusion.

Contingency plan for recruitment

A tracking data base will be developed to facilitate tracking and accurate reminders to the clinics included. In the process of initial contact with the clinics, a number of expected included participants will be estimated by each clinic. The clinic will make this estimate based on its patient demography,

which can be different across clinics e.g. some clinics will have a majority of young patients and others the opposite. This number will indicate a minimum for successful recruitment.

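### 504 slightly under-inflates 480 for a 5% loss (506 is needed), and the enrolment figure appears as both 500 and 504, so the number that ends recruitment is ambiguous

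*Protocol*

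**What the plan says.** The protocol's Sample-size section offers two rationales. The first combines the simulated P-values with a case count: 250 cases at an assumed 50% with pain at the primary follow-up. From this the protocol concludes "we decided on 500 subjects". No loss to follow-up is mentioned there.

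The second is an events-per-variable calculation, "assuming 50% has pain at follow-up and 20 events for each to be tested factor are needed". It adds: "The model should allow for 10-15 variables in a multivariable logistic regression analysis". The result is given as "This would lead to a sample size of 480", followed by "Assumed, 5% is lost to follow-up and we have a sample-size of 504 included participants".

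The FINER table also gives 500 as the adequate number. The section on recruitment of participants says the investigators "expect 500 participants in the ChiBPS cohort". It then says that, if the number from the sample-size calculations has not been recruited, "recruitment will continue until this number is reached". No figure is attached to that rule.

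**The concern.** There are two linked faults.

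- **Inflation.** Multiplying by 1.05 does not undo a loss of 5% of those enrolled. The operation that does is division by 0.95. The stated 504 therefore does not keep the 480 it was meant to protect.
- **Inconsistent target.** The rule for extending recruitment sends the reader to a section with two enrolment figures, 500 and 504. The figure that appears most often, 500, makes no allowance for the 5% loss that the same section assumes.

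What is at stake is whether the recruitment endpoint is clear and whether the sample-size statement can be reproduced. A reader should be able to tell when enrolment ends, and how many events and model parameters that number supports under the protocol's own assumptions.

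**Working it through.** **Inputs**, all from the Sample-size section: 20 events per factor, 50% with the outcome, 10–15 variables, 480 before allowance for loss, 5% loss, 504 included, and 500 subjects with 250 cases in the first rationale.

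**1. Reproducing 480.** Evaluable N = events per variable × variables / outcome proportion.

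- 10 variables: 20 × 10 / 0.5 = 400
- 12 variables: 20 × 12 / 0.5 = 480
- 15 variables: 20 × 15 / 0.5 = 600

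So 480 corresponds to exactly 12 variables. The protocol does not state that number; it is inferred from 480.

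**2. Reproducing 504.** 480 × 1.05 = 504 exactly. The inflation was n × (1 + d).

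**3. Correct inflation.** n / (1 − d) = 480 / 0.95 = 505.3. Check: 505 × 0.95 = 479.75, just short; 506 × 0.95 = 480.7. The figure is 506.

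**4. What each enrolment figure delivers** at 5% loss and 50% with the outcome:

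| Included | Evaluable (× 0.95) | Expected events (× 0.5) | Events / 20 | Whole parameters at 20 events each | Events per variable with 12 |
|---|---|---|---|---|---|
| 500 | 475.0 | 237.5 | 11.88 | 11 | 19.79 |
| 504 | 478.8 | 239.4 | 11.97 | 11 | 19.95 |
| 506 | 480.7 | 240.35 | 12.02 | 12 | 20.03 |

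**5. Shortfalls.**

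- Against 480 evaluable: 480 − 478.8 = 1.2 at 504, and 480 − 475 = 5 at 500.
- Against the 250 cases of the first rationale: 250 − 237.5 = 12.5 at 500. The figure of 250 holds only if nobody is lost.

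**6. The stated range of variables.** At 20 events each, the 237.5 events from 500 enrolled cover 10 or 11 variables. With 15 variables they give 237.5 / 15 = 15.8 events per variable. Fifteen at 20 each would need 600 evaluable, or 600 / 0.95 = 631.6, that is 632 included.

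**The case against.** The strongest reply is that nothing of practical consequence follows. The difference between 504 and 506 is two participants. With 480 evaluable and a 50% outcome, the standard deviation of the event count is √(480 × 0.25) = 10.95, so a deficit of 0.6 events (504) or 2.5 events (500) against 240 is far inside chance variation. The 50% and the 5% are round assumptions, and the protocol itself describes the analysis as explorative and the appendix calculations as provisional. All of this stands, and it is why the point is minor.

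Several stronger readings are tempting, but the documents do not support them:

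- *The target is given in three versions.* It is not. The 480 is the step before allowance for loss; only 500 and 504 are enrolment figures.
- *Recruitment will stop at a wrong number.* The rule names no number, and the 500 in that section is an expectation. The fault is ambiguity between two figures.
- *The protocol breaks its own rule for 12 variables.* It never commits to 12. At 500 enrolled, 10 or 11 variables still meet 20 events each, and both lie in the stated range.
- *Every 500 should become 506.* That would introduce an error. The appendix simulated n = 100, 200 and 500, so the P-value statement belongs to 500; and 506 × 0.5 = 253 would no longer match the 250-case reasoning.

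Nor would 506 secure 480 in the primary analysis, which the Statistical methods section places on first-time consulters, a subset whose share is not given.

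None of this removes the two faults in the text: the inflation is wrong as written, and the target is not unique.

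**Conclusion.** The point holds as a minor correction. Under the protocol's own 5% loss, 504 leaves 478.8 and not 480; the matching figure is 506. The other enrolment figure, 500, leaves 475 evaluable and 237.5 expected events, below both the 480 and the 250 cases attached to it. Because both figures stand in the section to which the recruitment rule refers, that rule does not identify a single endpoint.

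The shortfall is about 1 participant at 504 and 5 at 500, and by itself changes no analysis or conclusion. The more useful consequence is descriptive: at 20 events each, 500 enrolled supports at most 11 parameters, which is the lower end of the stated 10–15.

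These results take the 50% outcome proportion, the 5% loss and the 20 events per factor as given, and count the whole cohort. The inflation error does not depend on the inferred 12 variables, since 478.8 is below 480 whatever the variable count.

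**What to change.** Name one recruitment target in the section on recruitment of participants, and make the FINER table and the Sample-size section agree with it.

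- **Preferred: keep 500.** Drop 504 as an enrolment figure and state what 500 supports after 5% loss: 475 evaluable and about 237 events (in place of 250), hence at most 11 model parameters at 20 events each. Restrict the stated 10–15 variables accordingly. This needs no extra participants.
- **Alternative: correct 504 to 506** in the events-per-variable rationale only, say that 480 rests on 12 parameters, and name 506 as the target because it is the larger requirement. This means two more participants than 504 and six more than 500. The 250 cases should then be marked as the number before loss.

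Under either option, leave 500 unchanged where it reports the simulated sample size and its P-values. The change is to wording only; design, data collection and analysis are unaffected.

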(NVK) National Scientific Ethics Committee

Figure 1 Illustration of the timing of our study up to the point of publication and sharing of results.

Study setting

General practice clinics in Denmark.

Eligibility criteria for participation of participants and parents

Participants

The children and adolescents must have self-reported MSK pain at the time of recruitment and consult the GP in relation to their MSK pain. The primary reason for consultation may not necessarily be listed as MSK pain, but to be eligible for inclusion, MSK pain must be mentioned during the consultation with the GP. We do not have a pre-defined minimum or maximum MSK pain duration as a eligibility criteria and patients are eligible whether or not they have previously consulted their GP for their current MSK complaint.

We define MSK pain according to the International Association for the Study of Pain, IASP as: “pain arisen from muscle, tendon, bone, and joint”. Pain due to tumor, fracture, infection, or systemic and neurological cause will be excluded. Types of pain will be labelled according to the region affected, e.g. back pain, neck pain, shoulder pain, knee pain etc(33).

After consulting the GP in relation to MSK pain, inclusion and exclusion criteria will be applied as follows:

Inclusion criteria:

- 8 to 19 years
- Self-reported musculoskeletal pain

Traumatic pain caused by soft tissue damage, contusion or otherwise (excluding fracture), will be included.

Exclusion criteria:

- 0-7 or 20+ years
- Self-reported musculoskeletal pain due to tumor, fracture, infection, or systemic and neurological causes.

The inclusion and exclusion criteria will be determined at the following time-points:

1. During screening of the time schedule at the GP clinic
2. During the consultation with the GP
3. During a phone call made by the research assistant to either the participant or her/his parent, after retrieving their completed questionnaire from the GP clinic.

Parents

Parental participation will only be eligible after inclusion of their child. If a child is not eligible, or parental consent is not acquired on behalf of the child or adolescent <15 years of age, the parent will not be eligible for inclusion.

Declarations of consent

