Hereafter, data will be extracted from REDCap and transferred to a table similar table 1, which will then be anonymized through participant ID.

Statistical methods

Descriptive results will be stratified by sex and MSK pain type, presented with their central estimate and appropriate measure of dispersion (95% confidence interval CI). All descriptive statistics and test will be reported in accordance to the recommendations of the STROBE statement(29).

We will test the univariate association between each potential prognostic factor as well as combining the factors in a multivariable model to show the individual contributions.

The primary analysis will be done on those who has a first time consultation with their GP concerning their current MSK pain, but all consultations will be included.

The full statistical analysis plan will be developed concurrently and will be finalized before the last patient is enrolled. We minimize information bias by using identical questionnaires for all patients included, e.g. by asking both Danes and non-Danes whether they feel Danish or not.

Ethics and dissemination

The Ethics Committee of the North Denmark Region has waived the need for ethical approval of this study (date 090617). The Multidisciplinary Committee has approved the study and recommends Danish GPs to participate (ID: MPU 20-2017 / date 100117). We are currently applying their grant, to provide compensation to the included GPs for every recruited participant they provide to the study. The Danish Data Protection Agency has similarly granted access to the project (date 101717). All mentioned reviews are executed prior to protocol registration in ClinicalTrials.gov and to enrollment of the first participant (figure 1).

The adolescents included in the ChiBPS cohort will receive usual care, i.e. as usually administered at their GP. This study will not intervene in the diagnostic and therapeutic process.

The manuscript will be submitted for publication in an appropriate peer-reviewed journal. In addition to this we will produce material for distribution among general practitioners and other healthcare providers managing children and adolescents with MSK pain. This will be done by data visualization through social media, websites and patient associations. The included participants will also be offered knowledge sharing of study results, if interested.

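### The sample size is worked out for the whole cohort, but the primary analysis is placed on first-time consulters, a subset whose size the protocol never states

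*Protocol*

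**What the plan says.** Four parts of the protocol bear on this point.

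- **Sample-size.** With half the participants assumed to have pain later on, the events rule reads: "20 events for each to be tested factor are needed". On the planned size of the model, the section states: "The model should allow for 10-15 variables in a multivariable logistic regression analysis". The evaluable number is then given: "This would lead to a sample size of 480". Attrition is added last: "Assumed, 5% is lost to follow-up and we have a sample-size of 504 included participants". A parallel argument in the same section counts 250 cases among 500 subjects. Neither argument refers to consultation history.
- **Eligibility criteria, Participants.** "patients are eligible whether or not they have previously consulted their GP for their current MSK complaint". Appendix 1, item 1 asks whether this is the first consultation and offers a field for a later consultation number, so repeat consulters are expected.
- **Recruitment of participants.** The expected cohort is 500. If the calculated sample size has not been met, "recruitment will continue until this number is reached".
- **Statistical methods.** "The primary analysis will be done on those who has a first time consultation with their GP concerning their current MSK pain". The sentence ends: "concerning their current MSK pain, but all consultations will be included".

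The protocol gives no expected proportion or number of first-time consulters, and no enrolment target for them.

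**The concern.** The sample size and the primary analysis refer to different groups. The calculation uses everyone enrolled, while the primary analysis uses those attending for the first time with their current pain. Any repeat consulter counts towards the recruitment target but adds no event to the primary model.

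The closing clause of the Statistical methods sentence does not repair this. It does not say which analysis takes in the other consultations. On the ordinary reading, repeat consulters are enrolled and analysed outside the primary analysis, and then the Sample-size section does not size the primary analysis. If the clause instead brings everyone into the primary analysis, it cancels the first half of its own sentence.

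What is at stake is the plan's own safeguard against overfitting. The protocol adopts 20 events per factor, but a reader cannot tell from it how many variables the primary model may carry under that rule.

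**Working it through.** **Inputs from the Sample-size section:** outcome rate 0.50; 20 events per variable; 10 to 15 variables; 480 evaluable; 5% loss; 504 included.

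**Input not in the protocol:** f, the share of first-time consulters. An assumed range of 0.4 to 0.9 is shown. The 50% outcome rate is also assumed to hold in this subset.

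**Step 1: reproduce the stated size.** Evaluable N = variables × 20 / 0.50.

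- 10 variables: 10 × 20 / 0.50 = 400
- 12 variables: 12 × 20 / 0.50 = 480
- 15 variables: 15 × 20 / 0.50 = 600

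The stated 480 therefore corresponds to 12 variables. The protocol does not print 12, but no other count gives 480. For attrition, 480 × 1.05 = 504, as stated. In the other direction 504 × 0.95 = 478.8, so there is no spare margin.

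**Step 2: apply the restriction.**

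- Evaluable in the primary set = 480f
- Events = 480f × 0.50 = 240f
- Variables at 20 events each = 240f / 20 = 12f
- Enrolment that would keep 12 variables among first-time consulters = 504 / f

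| f (assumed) | Evaluable | Events | Whole variables at 20 events | Events per variable, 10 variables | Events per variable, 12 variables | Enrolment 504/f |
|---|---|---|---|---|---|---|
| 1.0 | 480 | 240 | 12 | 24.0 | 20.0 | 504 |
| 0.9 | 432 | 216 | 10 | 21.6 | 18.0 | 560 |
| 0.8 | 384 | 192 | 9 | 19.2 | 16.0 | 630 |
| 0.7 | 336 | 168 | 8 | 16.8 | 14.0 | 720 |
| 0.6 | 288 | 144 | 7 | 14.4 | 12.0 | 840 |
| 0.5 | 240 | 120 | 6 | 12.0 | 10.0 | 1008 |
| 0.4 | 192 | 96 | 4 | 9.6 | 8.0 | 1260 |

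**Step 3: threshold for the bottom of the planned range.** Ten variables need 10 × 20 = 200 events, so f must be at least 200 / 240 = 0.833. With 500 enrolled, evaluable N is 500 × 0.95 = 475, events are 237.5, and the threshold is 200 / 237.5 = 0.842.

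**Step 4: the other rationale.** The Sample-size section also relies on P-values below 0.05 at 500 patients. Appendix 5 simulates n = 100, 200 and 500 only, so most of the plausible sizes of the primary set lie between simulated points. As an illustration, take the Appendix 5 sex effect (odds ratio 1.78, half female, baseline odds 1). An unadjusted two-sided 5% comparison has power of about 88% with 480 participants, 74% with 336 (f = 0.7) and 59% with 240 (f = 0.5).

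**A separate limit, not caused by the restriction.** Even at f = 1, 13 variables need 13 × 20 / 0.50 = 520 evaluable and 15 need 600. Both exceed 480, so the upper part of the 10-to-15 range is not supported in the whole cohort either.

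**The case against.** The strongest reply is that the size of the problem is unknown. Nothing in the protocol shows that f is low. If at least 83% of participants are first-time consulters, a model at the lower end of the planned range still meets the 20-event rule. The 12 variables are inferred rather than stated, so falling short of 12 breaks no printed commitment. This stands as a limit on the claim: the mismatch is certain, but its practical size is not. It does not remove the mismatch, because 480 rests on 12 variables and the omission of f is what prevents a reader from judging.

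A second reply is that the statistical analysis plan, which the protocol says will follow and which is not at hand, may define the analysis sets and the final variable list. That is fair for those details. However, the sample size and the recruitment stopping rule are fixed in the protocol, and both refer to the whole cohort. The analysis plan need only be final before the last enrolment, which is late for changing the target.

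A third reply is that the Sample-size section calls the results explorative, and Appendix 5 labels its calculations provisional. This softens the consequence. The protocol nonetheless names a primary analysis and an explicit events rule, and the two should agree.

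**Conclusion.** The concern holds. The 480 evaluable and 504 included are correct arithmetic for 12 variables in the whole cohort. They describe the primary analysis only if every participant is a first-time consulter. For any f below 1 the primary model falls short of 12 variables at 20 events each, and below about 0.83 it cannot support even 10. The figures at particular values of f rest on two assumptions that the protocol does not supply: f itself, and a 50% outcome rate among first-time consulters. The point should be fixed. Given the explorative label and the unknown f, it is not shown to invalidate the study.

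**What to change.** 1. In Statistical methods, state which participants form the primary analysis, and say what the clause about all consultations means, for example which analysis includes the repeat consulters.
2. If the primary set is first-time consulters, restate the Sample-size section for that group: an assumed f with its basis, the expected events (480 × f × 0.50), and a number of primary-model variables no greater than the expected events divided by 20.
3. In Recruitment of participants, say whether the target counts all participants or first-time consulters only.

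Items 1 to 3 cost protocol wording only. The price is a less favourable stated figure: fewer than 12 variables for any f under 1, and fewer than 10 if f is under 0.83. If the sponsor prefers to keep 12 variables by counting the target in first-time consulters, that changes the study rather than the wording. Enrolment would rise to about 504/f, for example 560 at f = 0.9 or 840 at f = 0.6, and recruitment would take longer.
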